2.2.2 Secondary Endpoints

1. The secondary safety endpoints are the following:
 - a. The percentage of subjects experiencing the following events: SAEs, temporally-related AEs, increased risk scores for DVT or PE, TEEs, inhibitory anti-C1-INH antibodies, or clinically significant abnormalities in laboratory assessments (ie, lab abnormalities reported as AEs).
 - b. The percentage of administrations of CSL830 resulting in solicited local AEs (discomfort [eg, pain, burning], swelling, bruising, or itching at the CSL830 injection site).
 - c. The percentage of subjects who have at least 1 solicited local AE (discomfort [eg, pain, burning], swelling, bruising, or itching at the CSL830 injection site).
 - d. The percentage of subjects who become seropositive for HIV-1/-2, HBV, or HCV.

The secondary safety endpoints will be assessed for Treatment Period 1, Treatment Period 2 and Treatment Periods 1 and 2 (together). The secondary safety endpoints will also be assessed for the Extension Period (only) and for the treatment periods overall for subjects who are included in the Extension Period.

2. Efficacy endpoints considered as secondary include the following:
 - a. The percentage of subjects who experience a time-normalized HAE attack frequency of < 1 HAE attack per 4-week period.
 - b. The percentage of subjects who are responders. “Response” is defined as a $\geq 50\%$ relative reduction in the time-normalized number of HAE attacks during treatment with CSL830, compared with the time-normalized number of attacks that is used to qualify the subject for participation in this study (see [Section 4.1.2](#) [inclusion criterion 5]).

The secondary efficacy endpoints will be assessed for Treatment Period 1, and Treatment Periods 1 and 2 (together). The secondary efficacy endpoints will also be assessed for the Extension Period (only) and for the treatment periods overall for subjects who are included in the Extension Period.

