11.3.3.2 Secondary Safety Analyses

Adverse event data will be presented in individual listings and summary tables.

The number and percentage of subjects experiencing SAEs, temporally-related AEs, increased risk scores for DVT or PE, thromboembolic events, inhibitory anti-C1-INH antibodies, or clinically significant abnormalities in laboratory assessments during treatment will be summarized as defined above in [Section 11.3.3](#) and overall. The number and percentage of subjects who become seropositive for HIV-1, HIV-2, HBV, or HCV will be summarized as defined above in [Section 11.3.3](#) and overall. The number and percentage of subjects experiencing solicited local AEs, the number of solicited local AEs, and the number of solicited local AEs per administration will be summarized as defined above in [Section 11.3.3](#) and overall. The number and percentage of administrations of CSL830 resulting in solicited local AEs will be summarized as defined above in [Section 11.3.3](#) and overall. An overall summary of AEs will be given.

Temporally-related AEs will be defined as AEs which began within 24 hours of administration of CSL830. Note that temporally-related AEs are referenced as “suspected ADRs” in study CSL830_3001. Temporally-related AEs occurring during treatment will be summarized as defined above in [Section 11.3.3](#) and overall in the current study (CSL830_3002).

Summaries will include the number and percentage of subjects, the number of AEs, and the number of AEs per administration and per week (where applicable) and will also be summarized as defined above in [Section 11.3.3](#) and at study visits. Summaries by SOC and PT will also be presented.

Adverse events will also be described by intensity, relationship to CSL830, duration, and seriousness.

The safety analyses will be conducted for Treatment Period 1 (only), Treatment Period 2 (only), and for Treatment Period 1 and 2 (together). For the subjects who are in the Extension Period, the safety analyses will be conducted for the Extension Period and for the treatment periods overall.

11.3.4

CCI [Redacted]

CCI [Redacted]

CCI [Redacted]

[Redacted]

[Redacted]

CCI [Redacted]

[Redacted]

[Redacted]

[Redacted]

[Redacted]

CCI [Redacted]

[Redacted]

[Redacted]

[Redacted]

CCI [Redacted]
CCI [Redacted]

[Redacted]
[Redacted]

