2.2 Secondary endpoints

2.2.1 Secondary safety endpoints

The secondary safety endpoints are the following:

- AEs,
- Solicited AEs,
- Unsolicited AEs,
- SAEs,
- Temporally-related AEs (AEs which start within 24 hours of administration of the investigational product),
- Suspected adverse drug reactions (ADRs) (AEs which start within 24 hours of administration of the investigational product or which are related to investigational product administration including AEs with missing causality rating),
- The CSL830 injections followed by at least one solicited AE,
- Subjects reporting CSL830 injections followed by at least one solicited AE,
- Risk scores for deep vein thrombosis (DVT) or pulmonary embolism (PE),
- TEEs,
- Hypersensitivity,
- Anaphylaxis,
- Clinical laboratory assessments:
 - Hematology.
 - Biochemistry.
 - Urinalysis.
 - Coagulation profile.
 - Anti-C1-INH antibodies.
 - Viral serology.
- Vital signs including body weight,
- Physical examination.

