4.7.2.3 Analysis of Laboratory Findings

Normal ranges will be provided for laboratory tests. Values outside the normal range will be judged as clinically significant or non-clinically significant by the investigator. All abnormal laboratory data considered as clinically significant will be presented as AE.

All continuous laboratory parameters will be plotted against their scheduled assessments visits.

Analyses of haematology, biochemistry, and coagulation parameters will consist of the following:

- Descriptive statistics for baseline and each treatment visit, including changes from baseline to each treatment visit
- Mean values and the SD of the continuous laboratory parameters at each scheduled visit will be plotted against scheduled visits.

Baseline will be the assessment before the first injection (Week 1 Day 1) for all “CSL830-Naïve” and “CSL830-Interrupted” Subjects and “CSL830-Continuation” Subjects who did not complete the assessments at the CSL830_3001 End of Study Visit. For “CSL830-Continuation” Subjects who complete the assessments at the CSL830_3001 End of Study Visit, these assessments will be the baseline. If the baseline value for a subject is missing, no change from baseline will be calculated for the subject.

The number and percentage of subjects without anti-C1-INH antibodies and with anti-C1-INH antibodies (inhibitory, non-inhibitory and inhibitory and non-inhibitory combined) during the study will be summarized overall and for each study visit

Urinalysis, viral serology and pregnancy testing results will be listed only.

Notes:

- All results outside predefined normal ranges will be flagged as high or low in the data listings.
- Clinically significant laboratory values will be flagged in the listings.
- Unscheduled results will be listed only and not included in summary tables.

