4.7.5 Risk Assessment for Deep Vein Thrombosis and Pulmonary Embolism

The clinical model scoring system will be used for the risk assessment of deep vein thrombosis:

Clinical Feature	Score
Active cancer (treatment ongoing or within previous 6 months or palliative)	+1
Paralysis, paresis, or recent plaster immobilization of the lower extremities	+1
Recently bedridden for more than 3 days or major surgery, within 4 weeks	+1
Localized tenderness along the distribution of the deep venous system	+1
Entire leg swollen	+1
Calf swelling by more than 3 cm when compared with the asymptomatic leg (measured 10 cm below tibial tuberosity)	+1
Pitting edema (greater in the symptomatic leg)	+1
Collateral superficial veins (non-varicose)	+1
Alternative diagnosis as likely or greater than that of deep vein thrombosis	-2

Note: In subjects with symptoms in both legs, the more symptomatic leg is used.

Individual clinical feature scores and calculated risk scores will be recorded in the eCRF.

If a subject has a risk score of ≥ 1 , a lower extremity ultrasound examination will be arranged by the investigator to exclude deep vein thrombosis. If a deep vein thrombosis is confirmed on ultrasound examination, the event will be classified as an AESI and will be reported as a SAE.

The following clinical model scoring system will be used for the risk assessment of pulmonary embolism:

Clinical Feature	Score
Previous pulmonary embolism or deep vein thrombosis	+1.5
Heart rate >100 beats per minute	+1.5
Immobilization or surgery in the previous four weeks	+1.5
Clinical signs and symptoms of deep vein thrombosis (minimum of leg swelling and pain with palpation of the deep veins)	+3
Alternative diagnosis less likely than pulmonary embolism	+3
Hemoptysis	+1
Malignancy (on treatment, treated within the last 6 months, or palliative)	+1

Individual clinical feature scores and calculated risk scores will be recorded in the eCRF.

If a subject has a risk score of ≥ 2 , a computerized tomographic (CT) angiogram or appropriate investigation will be arranged by the investigator to exclude pulmonary embolism. If pulmonary embolism is confirmed on investigation, the event will be classified as an AESI and will be reported as a SAE.

The number and percentage of subjects with a risk score for deep vein thrombosis and pulmonary embolism of ≥ 1 or ≥ 2 (respectively) will be summarized at each visit.

CCI [REDACTED]

CCI [REDACTED]

[REDACTED]

[REDACTED]

[REDACTED]

[REDACTED]

[REDACTED]

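### SAP 4.7.5 summarizes DVT and PE risk scores only visit by visit, so the protocol's secondary endpoint, the percentage of subjects with increased scores during treatment, has no specified summary

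*SAP*

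**What the plan says.** **Protocol.** Section 2.2.2, item 1a, lists as a secondary safety endpoint "The percentage of subjects experiencing the following events: SAEs, temporally-related AEs, increased risk scores for DVT or PE", among others. It asks for the secondary safety endpoints in Treatment Period 1, in Treatment Period 2, in both together, in the Extension alone, and across all periods for Extension subjects. Section 11.3.3.2 plans the matching analysis, a subject count and percentage: "increased risk scores for DVT or PE, thromboembolic events, inhibitory anti-C1-INH antibodies, or clinically significant abnormalities in laboratory assessments during treatment will be summarized", by treatment grouping and overall. Section 8.1.2 sets a DVT score of at least 1 and a PE score of at least 2 as triggers for imaging or other investigation. Neither section defines an increased score.

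**SAP.** Section 2.2.1 names the endpoint only as risk scores; both the percentage of subjects and the idea of an increase are gone. Section 4.7.5 uses the two trigger values and says that subjects with a score "of ≥ 1 or ≥ 2 (respectively) will be summarized at each visit". Section 4.7.2 adds that secondary safety endpoints are shown by the dose actually taken, which fixes the columns of the table and not the statistic in it. Section 3.3.4 keeps unscheduled measurements out of summary tables.

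**The concern.** The two documents describe different quantities. The protocol asks how many subjects had an increased score at some time during treatment. The SAP asks how many were at or above the cut-off on each visit date. The second does not determine the first, because the same visit table arises whether one subject is positive throughout or a different subject is positive each time.

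If the SAP is followed as written, a pre-specified secondary safety endpoint is not reported, by dose or by period. A single raised score at one visit appears as one subject in one row and cannot be linked to other rows. A raised score found at an unscheduled visit appears in no table. Subjects already at the cut-off before dosing are not separated from those who reached it on CSL830.

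**Working it through.** **1. Is the visit table shorthand for both summaries?** For anti-C1-INH antibodies, SAP 4.7.2.3 says that results "during the study will be summarized overall and for each study visit". The SAP therefore writes out both levels where it intends both; SAP 4.7.5 gives only the visit level. SAP 4.14 declares other changes to the secondary safety analyses: grouping by actual dose, joint presentation of the periods, and removal of the dose-increase groups. Its readable text does not mention replacing the subject-level percentage for risk scores.

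**2. Can the endpoint be derived from the visit table?** The plan gives no figure for risk scores. Its only design figure (100 subjects, 3% event probability, 95% confidence; SAP 3.8) reproduces as 1 − 0.97^100 = 0.952, and nothing below depends on it.

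Inputs:
- Scheduled on-treatment scorings to Week 53 (Protocol 8.4.3 and 8.4.4): Weeks 9, 17, 25, 29, 37, 45 and 53, so V = 7.
- Later Extension scorings (Protocol 8.4.6): Weeks 12, 24, 36, 48, 60, 72, 84 and 88, so V = 7 + 8 = 15 for US Extension subjects only.
- Percentage at or above the cut-off at each visit, p. The documents give none, so 1%, 2% and 5% are assumed.

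For one score, with p the same at every visit and every subject scored each time, the percentage ever at or above the cut-off is:
- lowest, same subjects every time: p
- independent visits: 1 − (1 − p)^V
- highest, different subjects every time: min(1, V × p)

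| V | p | Lowest | Independent | Highest |
|---|---|---|---|---|
| 7 | 1% | 1% | 1 − 0.99^7 = 6.8% | 7% |
| 7 | 2% | 2% | 1 − 0.98^7 = 13.2% | 14% |
| 7 | 5% | 5% | 1 − 0.95^7 = 30.2% | 35% |
| 15 | 1% | 1% | 1 − 0.99^15 = 14.0% | 15% |
| 15 | 2% | 2% | 1 − 0.98^15 = 26.1% | 30% |
| 15 | 5% | 5% | 1 − 0.95^15 = 53.7% | 75% |

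Independence is not the upper bound; that is reached when no subject repeats.

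**3. In subjects.** With 2 of 100 at or above the cut-off at each of 7 visits, the endpoint could be 2/100 (Wilson 95% interval 0.6% to 7.0%) or 14/100 (8.5% to 22.1%). The visit table is the same in both cases. Among the roughly 50 subjects expected in the Extension, 1 of 50 at each of 15 visits could mean 1 subject (2%) or 15 subjects (30%).

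**The case against.** The case for leaving the SAP alone has several parts, and most of them limit the point.

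- **The cut-off is the protocol's own.** A reader might infer that a fixed cut-off is itself wrong and that the endpoint requires a change from the pre-dose score. The documents do not support this. An increased score is undefined, and the SAP uses the protocol's investigation triggers, which is a defensible reading. A PE score that goes from 0 to 1.5 is below the trigger, and nothing in the protocol says it must count.
- **Pre-existing risk.** A reader might infer that the scores consist largely of fixed history, so the same subjects would count at every visit. Both cancer items are time-limited and can lapse during the study. Only previous DVT or PE is permanent, and its 1.5 points do not reach the PE cut-off alone. Pre-dose scoring is also scheduled, so visit-level prevalence before dosing should be visible at least for subjects with a Screening Visit. What remains is narrower: the table does not link pre-dose and on-treatment status within a subject.
- **The count is recoverable.** SAP 4.1 puts all data in by-subject listings, so a hand count is possible. The table shells are a separate document and were not available, and part of the SAP is redacted. It would be wrong to say that the endpoint cannot be obtained; it is not specified as a summary in the readable text.
- **The primary endpoint is untouched.** A reader might infer that the thromboembolic primary endpoint is weakened. It does not use this table. Confirmed DVT or PE is an AESI and SAE, and SAP 4.7.1 analyzes thromboembolic events by person-time.
- **Joint presentation is declared.** SAP 4.14 does say that the periods are presented together, so part of the loss of period-specific results is disclosed. The loss of the subject-level percentage is not.

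None of this supplies the missing summary.

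**Conclusion.** The point stands in a limited form. The readable SAP specifies no summary of the percentage of subjects with increased DVT or PE risk scores during treatment, and the readable text of SAP 4.14 does not say that it was replaced. The visit table leaves the endpoint open by a factor of up to the number of visits: 1% to 7% over 7 scorings and 1% to 15% over 15 if 1% are at or above the cut-off each time, or 2% to 14% over 7 if it is 2%. These percentages rest on assumed prevalences, constant over time and with complete scoring. The ambiguity itself does not depend on the value chosen, provided any raised scores occur at more than one visit.

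The consequence is confined to one descriptive secondary safety endpoint. The change should be made because the protocol pre-specified the endpoint and the remedy is small.

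**What to change.** In SAP 4.7.5:

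1. Define an increased score, for example an on-treatment score at or above the protocol's cut-off in a subject who was below it before dosing.
2. Add the number and percentage of subjects with at least one such score, separately for DVT and PE, by actual treatment and for Treatment Period 1, Treatment Period 2, both together, and the Extension. State which period the Week 25 score belongs to, since SAP 3.1.3 excludes that visit from Treatment Period 1.
3. Include scores from unscheduled visits, as a stated exception to SAP 3.3.4.
4. Show subjects already at or above the cut-off before dosing separately. For CSL830-Continuation subjects use the CSL830_3001 End of Study score or the Day 1 score, as SAP 4.7.2.3 and 4.7.3 already do for laboratory values and vital signs.
5. Keep the visit table as supportive, and record the change in SAP 4.14.

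The cost is SAP wording and one table. No new assessment is needed: SAP 4.7.5 has item and total scores recorded in the eCRF. One check is required. Continuation subjects need not repeat the assessment on Day 1, so their CSL830_3001 scores must be available to the analysis.

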4.10 Adjustment for Covariates

Not applicable.

4.10.1 Center effects

The study is planned to be conducted at approximately 50 sites in North America, Europe, and other regions. Subjects from all centers will be pooled. No adjustment for center will be carried out.

4.11 Analysis Populations, Protocol Deviations

Prior to the database lock, any recorded deviations plus the following outputs will be reviewed to assess the impact on the efficacy, safety and QoL endpoints and to make decisions about the analysis populations:

- Listing of informed consent/assent (as appropriate) dates/times, screening evaluation dates and randomization dates/time
- Listing of eligibility and visit dates.
- Listing of any failed inclusion/exclusion criteria.
- Listing of subjects who discontinued the study.
- Listing of medical history.
- Listing of study drug injections showing any incomplete, missed injections and delayed injections.
- Listing of extent of exposure and treatment compliance.
- Listing of treatment compliance below 80% or above 120%.
- Listing of concomitant medications
- Listing of potentially prohibited concomitant medications with an indication including HAE prophylaxis (eg, IV C1-INH for prophylaxis, androgens, antifibrinolytics). Indication will be checked for other terms with the same meaning.
- List of oral medications for HAE prophylaxis (eg, androgens, progestins, antifibrinolytics) and if they were used at a stable dose for 3 months before Screening and at the same dose throughout the study.
- Listing of hormonal contraceptive regimen or hormone replacement therapy (ie, estrogen / progesterone containing product).
- Listing of subjects not treated.
- CCI [REDACTED]
- CCI [REDACTED]
- CCI [REDACTED]

- Listing of any subjects with one or two dose increases, with reason for dose increase and dates.

If needed, additional listings will be added.

If protocol deviations occur as outlined in the criteria above, then the data from complete individual subjects, individual visits or individual evaluations may be excluded from analysis populations.

The finalization of protocol violations and the final decision about excluded data will be made prior to the Database Lock and will be documented in the Data Review Meeting Minutes.

4.12 Handling of Missing Data

No imputation is planned. The primary safety endpoints are the person-time incidence rates of each primary endpoint safety event which are already taking into account that subjects' observation times can differ between subjects. Subjects receiving study drug will always have a certain amount of observation time and so will always contribute data/information to the primary safety endpoint independent if they discontinue early from the study or not. Only if a subject drops out before receiving any study drug this will lead to missing data for this subject, but this subject would not be included in the Safety Population anyway.

